2. INTRODUCTION

The Statistical Analysis Plan (SAP) has been written based on the Clinical Study Protocol (CSP) version 4.0 (13 December 2023).

The purpose of this document is to describe the procedures and the statistical methods to be applied in the data analysis and to ensure that the statistical methodologies that will be used are complete and appropriate to the study objectives.

The focus of this SAP is for the planned primary, secondary, and exploratory analysis at the final analysis in the study.

Pivotal and WuXi will perform the statistical analyses described in the protocol. Result of the analyses described in this SAP will be include in the Clinical Study Report (CSR).

2.1 Background & Rationale

Porphyria is a group of disorders resulting from deficient activity of specific enzymes in the heme biosynthetic pathway. Congenital erythropoietic porphyria (CEP), also known as Günther's disease, is a very rare inherited metabolic disorder resulting from a deficient activity of the enzyme uroporphyrinogen III synthase (UROIIIIS), the fourth enzyme in the heme biosynthetic pathway.

ATL-001 is a new oral formulation of ciclopirox olamine, including alginate and tocophersolan, currently under development for the treatment of subjects with CEP. This new oral formulation was developed to improve the local tolerance of ciclopirox olamine, which otherwise induces dose dependent gastrointestinal toxicity.

The present randomized, placebo-controlled, dose escalation, Phase I study aims to investigate the safety, tolerability, and PK of ATL-001 at five different dose levels in healthy subjects.

The results of this study are intended to be used to identify appropriate and well tolerated doses of ATL-001 to be used in further studies.

2.2 Study Objectives

2.2.1 Primary Objective

- To investigate the safety and tolerability of ATL-001 in healthy subjects.

2.2.2 Secondary Objectives

- To determine the PK of ATL-001 in healthy subjects

2.3 Study Design

[figure not shown]
This is a Phase I, double-blind, randomized, parallel-design, placebo-controlled, and dose escalation study to investigate the safety and PK of ATL-001 (ciclopirox olamine) in healthy subjects.

The study will consist of five sequentially recruited cohorts of 8 subjects each, resulting in up to 40 randomized subjects. Subjects will not be allowed to participate in more than one cohort.

Five different ATL-001 doses will be tested along with their matching placebos: ATL-001 0.2 mg/kg, ATL-001 0.5 mg/kg, ATL-001 1 mg/kg, ATL-001 2 mg/kg and ATL-001 4 mg/kg. All of them are named as IMP in this plan. On the morning of Day 1 to Day 5, each subject will receive a single oral dose of ATL-001 or placebo (i.e., total of 5 administrations of IMP) administered under fasting conditions (overnight fast; at least 10 hours). Refer CSP Section 8.1 for more details.

The day of the first administration of the IMP will be considered Day 1 of the study.

Study Schema (per cohort):

2.3.1 Randomization

At each investigated cohort, subjects will be randomized in the ratio of 6 active treatments to 2 placebos (3:1). For safety reasons, the subjects of each cohort will be divided in 2 sub-cohorts with 2 sentinel subjects in the first sub-cohort and 6 additional subjects in the second sub-cohort. The randomization schedule will be designed so that in each sub cohort there will be 1 subject scheduled to receive placebo. In order to maintain the double-blind study, the administration of the IMP must occur individually and separately, and in the absence of the physician responsible for the study. This is because the reaction after its administration could be easily distinguishable between placebo and ATL-001.

2.3.2 Study treatment

The product name is referred to as ATL-001. ATL-001, ciclopirox olamine oral solution, 20 mg/ml is a new oral formulation of ciclopirox. On the morning of Day 1 to Day 5, each subject will receive a single oral dose of ATL-001 or placebo (i.e., total of 5 administrations of IMP) administered under fasting conditions (overnight fast; at least 10 hours) following the instructions below:

| Cohort | Investigational medicinal product | Route | Administration Days |
|--------|-----------------------------------|-------|---------------------|
| 1 | ATL-001 0.2 mg/kg / Placebo | Oral | 1, 2, 3, 4, 5 |
| 2 | ATL-001 0.5 mg/kg / Placebo | Oral | 1, 2, 3, 4, 5 |
| 3 | ATL-001 1 mg/kg / Placebo | Oral | 1, 2, 3, 4, 5 |
| 4 | ATL-001 2 mg/kg / Placebo | Oral | 1, 2, 3, 4, 5 |
| 5 | ATL-001 4 mg/kg / Placebo | Oral | 1, 2, 3, 4, 5 |

2.3.3 Replacement of Subjects

In case of a withdrawn subject from the study, he/she may be replaced with another subject at the Sponsor's discretion. The replacement subject will be assigned to the same regimen dosage.

2.3.4 Follow up

The follow-up period will include 2 visits, one scheduled 3 days after the last IMP dose and one scheduled 30 days after the last IMP dose.

FU-V1 (3 days after the last IMP dose) and FU-V2 (30 days after the last IMP dose)

At both FU visits, the following activities and assessments will be performed:

- Assessment of changes in the medical history.
- Physical examination.
- Vital signs, including blood pressure, pulse rate and body temperature.
- Laboratory safety assessments, including hematology, biochemistry, and urinalysis.
- ECG.
- Concomitant medications.
- AEs.

2.3.5 Study Visits and Procedures

| | Screening period | Treatment period | | | | | | | | | | | | | Follow-up period | | |
|--|-------------------|--------------------|-----------------|-----------------|---------------|------------------|---------------|------------------|---------------|---------------|---------------|---------------|----------------|----------------|---------------------------------|--------------------------------|---------------------------------|
| | Screening visit | Hospital Admission | | | | | | | | | | | | | Hospital discharge ^f | FU-V1 | FU-V2 |
| Day | Day -30 to Day -1 | Baseline (Day 1) | Day 1 and Day 5 | | | | | | | | | | | | Day 2 and Day 6 | 3 days after the last IMP dose | 30 days after the last IMP dose |
| Assessment time | | Pre-dose (0 h) | 15 min (±5 min) | 30 min (±5 min) | 1 h (±10 min) | 1:30 h (±10 min) | 2 h (±10 min) | 2:30 h (±15 min) | 3 h (±15 min) | 4 h (±30 min) | 6 h (±30 min) | 8 h (±30 min) | 12 h (±30 min) | 24 h (±30 min) | | | |
| Informed consent | X | | | | | | | | | | | | | | | | |
| Inclusion/Exclusion criteria | X | X ¹ | | | | | | | | | | | | | | | |
| Randomization | | X | | | | | | | | | | | | | | | |
| Demographic data | X | | | | | | | | | | | | | | | | |
| Medical history | X | X ² | | | | | | | | | | | | | X ² | X ² | |
| Physical examination | X | X | | | | | X | | | | | | | X | X | X | |
| Vital signs ³ | X | X | | | | | X | | | | | | | X | X | X | |
| Laboratory safety assessments ⁴ | X | X | | | | | X | | | | | | | X | X | X | |
| Viral serology ⁵ | X | | | | | | | | | | | | | | | | |
| Drug of abuse and alcohol screen | X | X | | | | | | | | | | | | | | | |
| Pregnancy test (females only) ⁶ | X | X ⁷ | | | | | | | | | | | | | | | |
| ECG | X | X | | | | | X | | | | | | | X | X | X | |
| PK blood sampling | | X ⁷ | X | X | X | X | X | X | X | X | X | X | X | X | | | |
| Concomitant medications | X | X | X | X | X | X | X | X | X | X | X | X | X | X | X | X | |
| Adverse events ⁸ | X ⁹ | X ⁸ | X | X | X | X | X | X | X | X | X | X | X | X | X | X | |

ECG, electrocardiogram; FU-V, Follow-up Visit; h, hour; IMP, investigational medicinal product; min, minutes; PK, pharmacokinetics

[†] Subjects will be discharged at Day 2 and Day 6 after completing their assessments.

¹ Assessment of changes in inclusion/exclusion criteria

² Assessment of changes in the medical history

³ Vital signs include: blood pressure, pulse rate and body temperature

⁴ Laboratory safety assessments include: hematology, biochemistry, and urinalysis

⁵ Viral serology will comprise human immunodeficiency virus (HIV) I and II, hepatitis B virus surface antigen (HBsAg) and hepatitis C virus testing, and coronavirus disease (COVID)-19 testing by polymerase chain reaction (PCR)

⁶ Pregnancy testing of female subjects only. At screening pregnancy test will be done with using the blood sample; urine pregnancy test will be done on admission.

⁷ Also pre-dose at Day 5

⁸ Adverse events will be daily recorded by the subject in the subject diary and will not involve visit to the hospital.

⁹ Pre-treatment-emergent events.

2.4 Modifications made in the Statistical Analysis Plan

The following modifications have been made to the analyses specified in Protocol v4.0 (13 December 2023)

Screened population:

The definition of the Screened population has been added.

PK Analysis set:

Protocol definition:

PK analysis set are defined as all randomized subjects who received at least one dose of the study drug medication and have at least one valid PK measurement.

SAP definition:

PK analysis set are defined as all randomized subjects who received at least one dose of the study drug medication and have sufficient data to estimate at least one PK parameter. Subjects with major protocol deviations that might have impacted the PK data collection will be excluded from the population.

3. ANALYSIS POPULATIONS

The following analysis populations are described in the study protocol.

3.1 Safety Analysis Set

Safety analysis set are defined as all randomized subjects who receive at least one dose of the study medication regardless of if they have or have not completed the study.

Safety analyses will be based on Safety Analysis Set.

3.2 PK Analysis Set

PK analysis set are defined as all randomized subjects who received at least one dose of the study drug medication and have sufficient data to estimate at least one PK parameter. Subjects with major protocol deviations that might have impacted the PK data collection will be excluded from the population.

PK analyses will be based on PK analysis Set.

3.3 Other analysis sets

3.3.1 Screened population

The Screened population is defined as all screened subjects, including screening failures who are in the database.

Those subjects which did not pass the screening visit will not be randomized.

4. STUDY ENDPOINTS AND DERIVED VARIABLES DEFINITION

4.1 General considerations

The following time unit conversion factors will be applied to convert days into weeks, months, or years as needed.

Table 1 Time unit conversion factors

| | |
|---------|--------------|
| 1 week | 7 days |
| 1 month | 30.4375 days |
| 1 year | 365.25 days |

Table 2 Units conversion factors

| | |
|----------|-------------|
| 1 pounds | 0.453597 kg |
| 1 inch | 2.54 cms |

Periods:

Study day: The date of first dose of ATL001 administration is considered as Day 1 of the study.

For the events occurring on or after this day, the study day is calculated as the event date minus the date of the first administration of ATL001 plus 1 day.

For the events occurring before the start of treatment, study day is calculated as the event date minus the date of the first administration of ATL001.

The End of the study is defined as the date of the last study visit of a study subject (“last subject last visit”). The study will be completed after the last subject has performed the safety follow-up 30 days after the last IMP administration (FU-V2).

Baseline value: is defined as the last non-missing observation for each subject prior to the first administration of ATL001.

Difference from Baseline:

Change = Post baseline visit value – baseline value

If either the baseline or visit value is missing, the change from baseline is set to “missing”.

Placebo:

All placebo receiving subjects will be combined into a single placebo group and presented as “Placebo” group.

4.2 Baseline and Demographics Characteristics

Age: The information of the variable age will be shown and analysed continuously and categorized according to the following distribution.

- < 18
- [18, 40)
- [40,65]
- >65

Weight: will be displayed in kilograms.

Height: will be displayed in centimetres.

Result of Urine drug screen:

- **Positive:** if result of any urine test is positive in any of the following substances, we will consider the test 'Positive'

Amphetamine/Barbiturates/Benzodiazepine/Ethanol/Cocaine/Opiate/Phencyclidine/Cannabinoids/Cotinine

- **Negative:** if the result of all urine tests is negative in the following substances, we will consider the test "Negative"

Amphetamine/Barbiturates/Benzodiazepine/Ethanol/Cocaine/Opiate/Phencyclidine/Cannabinoids/Cotinine

- **Not determined:** if the result is neither positive nor negative based on the above definitions (some or all of the tests have a ND result)

4.3 Prior and Concomitant medications

Prior medications: are defined as medications that started within 8 weeks prior to the Screening Visit (whether continuing or not).

Concomitant medications: are defined as any medications taken after the first administration of ATL001 through last study visit.

4.4 Efficacy Endpoints

This is a Phase I study in healthy subjects. The efficacy of the IMP will not be tested.

4.5 Safety Endpoints

4.5.1 Treatment exposure

Compliance (%): will be calculated as the percentage of actual doses the subject took with respect to the total doses planned.

4.5.2 Adverse events

Adverse events

- **Non-TEAE** is an AE that occurs prior to the initiation for the treatment.
- **TEAE** is an AE that occurs after administration of the first dose of ATL001 and through 30 days after the last dose of ATL001 administration. A TEAE also includes an AE present prior to administration of IMP which worsened after administration of IMP.

Note: If an AE date of onset is incomplete, an imputation rule will be used to classify the AE as treatment-emergent or not. The algorithm for imputing date of onset is provided in the section Handling of Missing Data.

Related to ATL-001:

- **Related**: TEAEs with relationship to study treatment (as recorded on the AE eCRF page), Relationship (“Definite” / “Probably” / “Possibly”) reported by the investigator and those of missing or unknown relationship.
- **Not Related**: TEAEs with relationship to study treatment (as recorded on the AE eCRF page), Relationship (“Unlikely” / “Unrelated”) reported by the investigator.

4.5.3 Laboratory results

4.5.3.1 Urea

Urea values will be calculated based on the standardised BUN values reported in the database.

The conversion factor to be applied for this calculation is:

$$\text{Urea (mmol/L)} = \text{BUN(mmol/L)} * 2.1428$$

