13.1.4.2 Tolerability

Descriptive statistics will be calculated for the quantitative variables obtained in the vital signs records, ECG, physical examination and laboratory safety tests (hematology, biochemistry and urinalysis).

Vital Signs

Vital signs data will be presented by individual listings with flagging of abnormal values. Vitals signs data will be summarized by visit and treatment group, together with changes from baseline.

Electrocardiogram

Overall interpretation of ECG results (i.e., normal or abnormal) will be summarized. In addition, standard ECG parameters will be summarized by treatment group, together with changes from baseline.

Physical Examination

Physical examination data will be summarized by treatment group.

All abnormal physical findings will be listed.

Laboratory Safety Assessments

For laboratory data (hematology, biochemistry, and urinalysis), summary statistics will be produced for observed values and for changes from baseline to each visit. In addition, the number of abnormal and clinically significant observations will be tabulated for each treatment group by visit. Abnormal values will be flagged in listings.

Shift tables will be created for a subset of laboratory parameters, which will be defined in the SAP. Shift tables will show the number of subjects who changed from below, within or above the reference range at baseline to below, within or above the reference range at each time of assessment.

For laboratory values which are below the limit of quantification, the value corresponding to the limit of quantification will be used when summarizing data.

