5.4.3.4 Clinical Laboratory Test

To evaluate the safety profile the following laboratory tests will be performed:

- **Hematology**

- Hemoglobin
- Erythrocytes
- Leukocytes
- Neutrophils
- Lymphocytes
- Monocytes
- Eosinophils
- Basophils
- Ferritin
- C reactive protein (CRP)

- **Biochemistry**

- Alkaline phosphatase
- AST / SGOT
- ALT / SGPT
- Gamma-glutamyl transferase
- Creatinine
- Glucose
- Total Bilirubin
- Lactate dehydrogenase
- Triglycerides
- Calcium
- Chloride
- Potassium
- Sodium
- TSH
- BUN

- **Urinalysis**

- Quantitative
 - pH
 - Specific gravity
 - Microalbumin
 - Protein
- Qualitative
 - Urine bilirubin (Positive / Negative /Not Done)
 - Ketones (Positive / Negative /Not Done)
 - Nitrite (Positive / Negative /Not Done)
 - Occult blood (Positive / Negative /Not Done)
 - Acid Urate Crystals (Positive / Negative /Not Done)
 - Urine glucose (Positive / Negative /Not Done)
- Microscopic analysis quantitative (will be analyzed as qualitative)
 - RBC Casts (in range / above the range/ missing)
 - WBC Casts (in range / above the range/ missing)
- Microscopic analysis qualitative
 - Urine Appearance (Normal / Abnormal /Not Done)
 - Urine Color (Normal / Abnormal /Not Done)

For each parameter, summaries will be presented for the Screening, Baseline, and each scheduled post-baseline visit.

For each quantitative laboratory parameter, the values, and changes from baseline will be summarized by placebo / dose-level cohorts (including number of observations, missing, mean, SD, median, Q1, Q3, minimum, and maximum) will be calculated for each visit.

The decimal precision for each parameter will be based on the maximum number of decimals to which the results were reported on the eCRF.

If a result for a parameter that is normally considered quantitative is reported as a range (i.e., the result for basophils is reported as '<0.01'), this value will be not considered in the summary table. All the values reported will be included in the respective listing.

Lab Original results with ND/ NA/ NE/ UNK/ NQ/ UN etc: will not be evaluated or used for the analysis purpose.

All biochemistry, hematology, and urinalysis data will be listed.

The listings will be sorted by placebo /dose-level cohort, subject, parameter, visit and timepoint (if applicable).

The results and normal ranges will be displayed to the same decimal precision in the listings.

The clinically significant abnormal values will be flagged.

Notes:

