- Clinical laboratory data will be analysed using standardized values.
- Only evaluable data will be used, and missing data will not be imputed.
- The Microscopic analysis quantitative parameters will be analysed as categorical variable.
- Biochemistry: FSH and Glomerular Filtration Rate will be shown in a listing.

Information on the derived variable Urea will be presented. The standardised values and changes from baseline will be summarised by placebo / dose level cohorts (including number of observations, missing, mean, SD, median, Q1, Q3, minimum and maximum) and will be calculated for each visit.

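### The SAP's urea formula applies a mass ratio (2.1428) between two molar units, so derived urea is about 2.14 times too high as written; separately, the SAP's rule for '<x' laboratory results departs from the protocol without being listed

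*SAP*

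**What the plan says.** **Urea.** SAP 4.5.3.1, added in version 2.1, states that "Urea values will be calculated based on the standardised BUN values reported in the database". It gives urea in mmol/L as "BUN(mmol/L)} * 2.1428". The notes to SAP 5.4.3.4 add that "Clinical laboratory data will be analysed using standardized values" and, for derived urea, that "The standardised values and changes from baseline will be summarised by placebo / dose level cohorts", at each visit. BUN is also in that section's list of biochemistry tests, so both quantities are tabulated. Neither document says how BUN in mmol/L was obtained.

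**Results reported as '<x'.** For laboratory values below the limit of quantification, protocol 13.1.4.2 says that "the value corresponding to the limit of quantification will be used when summarizing data". SAP 5.4.3.4 says of a result such as '<0.01' that "this value will be not considered in the summary table"; it is kept in the listing. SAP 2.4 opens with "The following modifications have been made to the analyses specified in Protocol v4.0" and then names only the Screened population and the PK analysis set.

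**The concern.** A factor of about 2.14 is the familiar conversion from urea nitrogen to urea when both are expressed as mass. Here both sides carry a molar unit. One urea molecule contains one pair of nitrogen atoms, so the two amounts are equal in mmol/L and no such factor belongs there.

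The line feeds reported output. Urea is a protocol laboratory parameter (Table 12), the SAP's test list has BUN in its place, and this derivation is how the protocol's urea is delivered. Laboratory safety is part of the primary endpoint. Protocol 6.2.1.3 describes mainly renal excretion, and Table 12 has eGFR at Screening only, so the post-dose BUN, urea and creatinine summaries are the tabulated renal markers. Wrong urea levels and absolute changes would go into the study report.

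The '<x' rule is a separate matter. The two documents prescribe different handling, and dropping only low values raises the mean and reduces n in groups that are already very small.

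**Working it through.** **Inputs.** The factor 2.1428 and both mmol/L units come from SAP 4.5.3.1. The molar masses are basic chemistry, assumed here because the documents do not give them: urea 60.056, two nitrogen atoms 28.014, one nitrogen atom 14.007 g/mol. The BUN of 14 mg/dL is an assumed example.

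**Step 1: reproduce the factor.** 60/28 = 2.1429; with finer masses, 60.056/28.014 = 2.1438. The SAP's 2.1428 is this mass ratio, correct to about 0.05%. Used properly, 14 mg/dL BUN x 2.1428 = 30.0 mg/dL urea.

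**Step 2: the molar factor.** 14 mg/dL is 140 mg/L of urea nitrogen, and 140/28.014 = 5.00 mmol/L of nitrogen pairs, hence 5.00 mmol/L of urea. The factor is 1.

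**Step 3: the SAP formula under each possible meaning of the standardised BUN** (true urea 5.00 mmol/L):

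| Meaning of the BUN field | BUN value | x 2.1428 | Result |
|---|---|---|---|
| A. Usual mmol/L (nitrogen pairs): 140/28.014 | 5.00 | 10.7 | Urea 2.14 times too high |
| B. mmol/L of single nitrogen atoms: 140/14.007 | 10.0 | 21.4 | Urea 4.29 times too high |
| C. Divided by urea's molar mass: 140/60.056 | 2.33 | 5.0 | Urea right, BUN 2.14 times too low |
| D. Still in mg/dL | 14 | 30.0 | Both right as mg/dL; 6.0 times too high if read as mmol/L |

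Under A and B derived urea is wrong; under C the BUN table is wrong; under D the unit labels are wrong.

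**Step 4: change from baseline under A.** BUN rising from 14 to 18 mg/dL is a true change of 40/28.014 = 1.43 mmol/L. The SAP reports 1.428 x 2.1428 = 3.06 mmol/L. The percent change is 4/14 = 28.6% either way.

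**Step 5: the '<x' rule.** Let k of n values lie below limit L, and let m be the mean of the retained values. The SAP mean is m. The protocol mean is [(n - k)m + kL]/n. The difference is (k/n)(m - L). Each excluded value therefore moves the mean by 1/6 of the gap m - L in an active cohort of 6, and by 1/10 in the pooled placebo group (5 cohorts x 2 = 10). As an illustration with assumed values, take two of six results at '<0.01' and four averaging 0.04:

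- SAP: 0.040, with n = 4.
- Protocol: (4 x 0.04 + 2 x 0.01)/6 = 0.030, with n = 6.

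**Step 6: effect on changes.** SAP 4.1 says "If either the baseline or visit value is missing, the change from baseline is set to" missing. If a '<x' baseline is handled as missing, that subject leaves the change summary, unless a numeric Screening value is taken as baseline. The same subject's quantifiable post-dose value stays in the observed-value summary.

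**The case against.** **The 2.14 is conditional.** The documents do not define the standardised BUN field, and the readings run from no error in urea to a factor of 6. If both labels are slips for mg/dL, the factor is right and nothing needs recalculating. This stands as a limit on the size: 2.14 applies to the printed units with their usual meaning. It does not rescue the line, since correcting the labels is itself a correction.

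**The reporting unit is not established.** SAP 5.4.3.4 lists BUN without a unit, and the urea row of protocol Table 12 is broken in the text available here, so it neither confirms nor excludes a repair. This too stands. The table's biochemistry unit lists do contain mg/dL entries, so a check against mg/dL results is a reasonable start, but the site unit should be confirmed first.

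**The consequence is small.** The trial is descriptive. A constant multiplier leaves between-group ratios and percent changes intact. BUN and creatinine are summarised separately. Clinical significance is judged on recorded values (protocol 11.4.6), and the stopping rules and dose-limiting toxicity criteria do not use urea summaries. All of this is correct and keeps the point from ranking higher.

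**The '<x' point is different in kind.** It is a documentation inconsistency, its frequency is unknown, and the loss of changes from baseline is an inference, because the SAP does not say outright that such values are set to missing. Protocol 13.3 also allows a deviation to be described in a revised SAP or the final report. Those limits are fair, but 13.3 also asks for a justification, and the SAP gives none.

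**Conclusion.** The formula is wrong as written. With the printed units and the usual meaning of BUN in mmol/L, derived urea is 2.14 times too high in every group, and so are its SDs and absolute changes. While both units stay mmol/L, no convention gives a correct BUN and a correct urea. The exact size depends on how BUN was standardised, which the sponsor can settle from the data. The harm is confined to reported urea levels and absolute changes (or to the BUN table, under reading C); comparisons on a ratio scale and the safety decision rules are unaffected. It should be fixed before the tables are relied on.

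The '<x' conflict between protocol 13.1.4.2 and SAP 5.4.3.4 is real and unlisted in SAP 2.4. It is the lesser point, and its size depends on the fraction of results below the limit, which the documents do not give.

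**What to change.** **SAP 4.5.3.1**

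1. Confirm the site's reporting unit for BUN. If it is mg/dL, divide the standardised BUN by the reported result: about 0.357 indicates reading A, 0.714 B, 0.167 C and 1.0 D.
2. Either standardise BUN as mg/dL x 0.357 and set urea (mmol/L) equal to BUN (mmol/L), or keep 2.14 and apply it only from mg/dL to mg/dL. With the first option the urea table repeats the BUN table, so one table labelled for both would do.
3. Re-run any urea tables produced under version 2.1. Re-run the BUN tables as well if B, C or D holds and BUN is re-standardised at 0.357; under D, relabelling both as mg/dL is enough if that unit is kept.

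**SAP 5.4.3.4**

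Apply the protocol's limit-value rule in summaries and in changes from baseline, and show the number of results below the limit. Otherwise, list and justify the departure in SAP 2.4.

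**Cost.** One formula line, one check of the BUN standardisation, one sentence on '<x' results and a re-run of the affected laboratory tables.
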